1.0 Objectives

1.1 Study Objectives

Describe the purpose, specific aims or objectives. State the hypotheses to be tested.

This mixed-methods study will evaluate the impact of the Research-to-Policy Collaboration (RPC) model on the use of scientific research in federal policymaking. Human Subjects research will be carried out to assess the RPC effects on participating researchers who are trained and coached by the model to respond to current policy opportunities and translate scientific research to public officials.

A survey will be used to assess researchers reported policy competencies and motivation for conducting policy-relevant research. This study will also examine whether these outcomes vary as a function of collaborative experiences with public officials and hypothesizes that more productive and satisfying collaborations will improve researchers' ongoing policy engagement and increases in policy-relevant research. These surveys will be supplemented by qualitative interviews to discuss researchers' experiences translating research and working with public officials. This includes discussion of (1) barriers and facilitators of participating in researcher-public official partnerships, (2) the types of interactions between researchers and public officials facilitated by the RPC, and (3) how the RPC affects researchers' assumptions about and interactions with public officials.

1.2 Primary Study Endpoints

State the primary endpoints to be measured in the study. Clinical trials typically have a primary objective or endpoint. Additional objectives and endpoints are secondary. The endpoints (or outcomes), determined for each study subject, are the quantitative measurements required by the objectives. Measuring the selected endpoints is the goal of a trial (examples: response rate and survival).

This study will measure changes in participants' policy knowledge and skills, policy engagement, and the extent to which research activities are informed by public officials' needs.

1.3 Secondary Study Endpoints

State the secondary endpoints to be measured in the study.

Experiences collaborating with public official will be assessed among participants in the RPC intervention (experimental) condition. Aspects of these collaboration experiences that will be measured include satisfaction, perceived value and impact, and trust and respect.

2.0 Background

2.1 Scientific Background and Gaps

Describe the scientific background and gaps in current knowledge.

The persistent gap between research and policymaking is a multifaceted challenge borne in part out of limited interaction between researchers and public officials. Yet, interaction without adequate preparation for policy engagement (i.e., training and supports) may thwart researchers' efforts to support public officials' use of empirical evidence. Although varied policy training approaches for researchers exist, little empirical work has explored their effectiveness in improving policy knowledge and skills or supporting researchers' enduring policy engagement. Furthermore, scant research has considered the extent to which facilitating policy experiences among researchers may shift researchers' perspectives on how research evidence is produced, communicated, and disseminated.

2.2 Previous Data

Describe any relevant preliminary data.

N/A

2.3 Study Rationale

Provide the scientific rationale for the research.

The RPC model is based on a growing literature around the use of scientific evidence in policymaking, which emphasizes the need to cultivate positive interactions and collaborations between researchers and public officials. A prominent facilitator for public officials' use of research is the translation of relevant scientific findings in the context of trusting relationships with researchers. Public officials often turn to "experts" when addressing issues that are part of a political agenda. Therefore, connecting researchers to current policy opportunities and priorities in ways that engender trusting relationships aligns with known facilitators of public officials' use of research evidence. However, such connections must be made tactfully, and enhancing researchers' policy competencies can strengthen the success of their policy outreach.

The success of connections between public officials and researchers may be improved by strengthening researchers' policy knowledge and skills. Much more research is needed to evaluate training approaches and enhance their effectiveness. Specifically, research is needed that evaluates the impact of training approaches by longitudinally tracking researchers' reported confidence and skills, participation in policy efforts, and interactions with public officials. Efforts are also needed to explore the extent to which researchers' policy competencies translate into public officials' increased utilization of research findings.

In addition to supporting public officials' use of research evidence, researcher-public official partnerships may have the potential to improve the usefulness of research activities for public officials. Few supports are in place to help researchers proactively consider policy and practice implications prior to study development, even though research that is responsive to public officials' needs may be more likely to be used by public officials in the future. Policy-informed research adjusts to prevailing policy priorities, shaping the questions that are investigated and how results are interpreted and communicated. A cultural shift toward more policy-informed research is needed, including the way it is produced, interpreted, and communicated—and opportunities for researcher-public official collaboration may support this shift. Some studies have shown that co-creation of research knowledge can strengthen the utility of findings for policymaking and implementation. However, the majority of partnerships applying research in a decision-making context focus on producing generating timely and actionable research, whereas there is a need to complement this knowledge base by investigating subtler partnerships in which research is distilled for co-interpretation of policy implications.

3.0 Inclusion and Exclusion Criteria

Create a numbered list below in sections 3.1 and 3.2 of criteria subjects must meet to be eligible for study enrollment (e.g., age, gender, diagnosis, etc.). Indicate specifically whether you will include any of the following vulnerable populations: (You may not include members of these populations as subjects in your research unless you indicate this in your inclusion criteria.) Review the corresponding checklists to ensure that you have provided the necessary information.

- **Adults unable to consent**
 - Review "CHECKLIST: Cognitively Impaired Adults (HRP-417)" to ensure that you have provided sufficient information. HRP-417 can be accessed by clicking the Library link in CATS IRB (<http://irb.psu.edu>).
- **Individuals who are not yet adults (infants, children, teenagers)**

- If the research involves persons who have not attained the legal age for consent to treatments or procedures involved in the research (“children”), review the “CHECKLIST: Children (HRP-416)” to ensure that you have provided sufficient information. HRP-416 can be accessed by clicking the Library link in CATS IRB (<http://irb.psu.edu>).
- **Pregnant women**
 - Review “CHECKLIST: Pregnant Women (HRP-412)” to ensure that you have provided sufficient information. HRP-412 can be accessed by clicking the Library link in CATS IRB (<http://irb.psu.edu>).
- **Prisoners**
 - Review “CHECKLIST: Prisoners (HRP-415)” to ensure that you have provided sufficient information. HRP-415 can be accessed by clicking the Library link in CATS IRB (<http://irb.psu.edu>).
- **Neonates of uncertain viability or non-viable neonates**
 - Review “CHECKLIST: Neonates (HRP-413)” or “CHECKLIST: Neonates of Uncertain Viability (HRP-414)” to ensure that you have provide sufficient information. HRP-413 and HRP-414 can be accessed by clicking the Library link in CATS IRB (<http://irb.psu.edu>).

3.1 Inclusion Criteria

List the criteria that define who will be included in your study.

Researchers who voluntarily enlist in the RPC will be asked to participate in the trial. All participants will be over 18 years old.

3.2 Exclusion Criteria

List the criteria that define who will be excluded in your study.

None.

3.3 Early Withdrawal of Subjects

3.3.1 Criteria for removal from study

Insert subject withdrawal criteria (e.g., safety reasons, failure of subject to adhere to protocol requirements, subject consent withdrawal, disease progression, etc.).

Researchers who choose to stop participating in the study or the RPC itself. All study participants can choose to opt-out of the study at any time.

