3.3.2 Follow-up for withdrawn subjects

Describe when and how to withdraw subjects from the study; the type and timing of the data to be collected for withdrawal of subjects; whether and how subjects are to be replaced; the follow-up for subjects withdrawn from investigational treatment.

No follow-up will be conducted with withdrawn subjects.

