7.0 Study Design and Procedures

7.1 Study Design

Describe and explain the study design.

This human subjects research involves a longitudinal randomized controlled trial and depth interviews of researchers who participate in the Research-to-Policy Collaboration (RPC). Researchers are recruited to participate in the RPC. When a researcher voluntarily enlists in the RPC, they provide information about themselves and their expertise as part of RPC implementation. Subsequently, RPC participants are invited to participate in the study. Those who agree to participate are randomly assigned to either the RPC intervention group or a blinded control group that receives a “light touch” intervention. The next step of RPC implementation involves creating a discussion forum for engaging researchers in training or policy efforts. Different discussion forums will be used for each group: the RPC group (including those in the study who were assigned the intervention as well as those who refused to participate in the study) and the control group. The control group will receive information sheets regarding how to engage in policy, whereas the RPC group will be actively engaged in a series of six voluntary one-hour webinars preparing researchers for policy engagement, and will receive solicitations for contributing to policy efforts via the discussion forum. These activities are designed to build researchers’ capacity for successful collaborative interactions with congressional staff around *current policy priorities* and *specific, time-sensitive needs* of congressional offices.

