Those in the RPC group who have expertise related to current congressional priorities and needs may be invited to participate in a Rapid Response Event, which brings researchers and congressional staff together face-to-face to meet in congressional offices (Washington, DC) and plan a collaborative response to a current policy issue. To clarify expectations for involvement and minimize the threat of disappointing those who are not invited to the Rapid Response Event, all RPC participants are repeatedly informed throughout the capacity-building stage (via trainings and the discussion forum) that this selection process will occur based on their participation in trainings, web-based engagement, and a match between their expertise and congressional needs. Subsequent to these meetings, RPC participants work collaboratively with one another and the congressional office to respond to the current policy issue.

Participation in the study is voluntary among those enlisting in the RPC; opting out of the survey will not impact their ability to participate in the intervention. Study participants are asked to complete the survey approximately every three months for about one year: (1) Baseline, (2) Subsequent to training, (3) Subsequent to policy engagement, and (4) Follow-up. Twenty-two study participants in the intervention group will be asked to complete in-depth qualitative interviews regarding their experiences: 11 will participate prior to RPC involvement and 11 will participate subsequent to their RPC involvement. Qualitative interviews will be recorded and transcribed.

Observations of public meetings may involve three types of participants: (1) public officials, (2) researchers who have consented to study participation, and/or (3) researchers who are involved in the intervention but did not consent to study participation. Public meetings include: (1) those that occur in

public officials' offices, which are located in congressional office buildings that are open to the public (i.e., any member of the public may visit any office at any time), and (2) online trainings that are open to the public, accessible through a URL on a publicly available website.

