7.2.2 EXAMPLE: Visit 2 or Day 2 or Post-test, etc. (format accordingly)

Provide a description as defined above and format accordingly.

The same survey protocol as used in the pre-test will be administered approximately every three months for about one year: (2) Subsequent to training, (3) Subsequent to policy engagement, and (4) Follow-up. Efforts to minimize survey attrition will include tracking non-responses to follow-up surveys and requesting survey participation via individual emails twice per week until survey completion or until the 3-week window for survey participation ends or until the participant opts-out of participating in the survey. In the last week of the survey window, survey participants who have not yet participated or opted-out of participation will be contacted by phone to request their participation and to complete the survey over the phone if needed.

Qualitative interviews will occur subsequent to the RPC implementation, approximately 9 months following study enrollment, using web-chat or phone. These interviews will ask:

- How did you become involved in the RPC? Is this your first involvement with policy? With legislation? If no, what are your previous experiences?

- What were your expectations and aspirations from involvement in the RPC?
- Can you describe the interactions you've had with policymakers through the RPC? (e.g. informal coffees, phone calls, formal meetings, etc). How does this compare to interactions outside the RPC?
- What kinds of evidence have you seen and used as part of the RPC? How? Did this reflect your expectations?
- What has worked well? What could have gone better? (Risks of interaction, perceptions and stereotypes)

This study also involves non-human research data, drawing from public information regarding public officials' use of research evidence, which will be obtained from legislators' sponsored bills, public statements, and reported research use by public officials. Non-human research data will also support the interpretation of key findings from the current investigation that involve human subjects.

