7.3 Duration of Participation

Describe the duration of an individual subject's participation in the study.

Study participation lasts for up to two years or until the participant opts-out of the study.

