8.0 Subject Numbers and Statistical Plan

8.1 Number of Subjects

Indicate the total number of subjects to be accrued.

If applicable, distinguish between the number of subjects who are expected to be enrolled and screened, and the number of subjects needed to complete the research procedures (i.e., numbers of subjects excluding screen failures.)

We aim to enroll a maximum of 300 researchers in the baseline period of this study. The target number of study participants in the full study is 80, including 40 researchers in the intervention and 40

researchers in the control group. This level of oversampling is required because not all researchers will complete all phases of the intervention and oversampling will combat attrition from study participation.

Twenty-two researchers from the intervention group will be selected to participate in depth-interviews (11 at pre-test and 11 at post-test). Researchers will be sampled purposively such that the sample is representative of those with or without prior policy experience and range in their attitudes toward policy engagement (e.g., skeptical or positive), which will be determined by survey data from the first time point.

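### Stopping the RPC counts as leaving the study, so later surveys are lost from randomised researchers who might still answer

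*Protocol*

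**What the plan says.** Protocol 3.3.1 gives the removal criterion as "Researchers who choose to stop participating in the study or the RPC itself". Leaving the study and leaving the intervention are joined by 'or', so either is enough. The next sentence of 3.3.1 gives a separate right to opt out of the study at any time. Protocol 3.3.2 then says "No follow-up will be conducted with withdrawn subjects". The template prompt above that answer asks, among other things, about follow-up of subjects withdrawn from the investigational treatment.

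Other sections treat the study and the RPC as separate:

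- Protocol 7.1 says that "opting out of the survey will not impact their ability to participate in the intervention". No matching rule keeps people who leave the RPC in the surveys.
- Protocol 7.2.2 sends survey reminders until completion, the end of a three-week window, or "until the participant opts-out of participating in the survey".
- Protocol 7.3 says "Study participation lasts for up to two years or until the participant opts-out of the study".

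Neither 7.2.2 nor 7.3 mentions stopping the RPC. Protocol 8.1 expects some non-completion of the intervention and answers it with numbers: "not all researchers will complete all phases of the intervention and oversampling will combat attrition from study participation".

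**The concern.** Stopping an intervention and withdrawing from data collection are different events. Researchers are randomised when they agree to the study, before the RPC is delivered (Protocol 4.1 and 7.1), so anyone removed for stopping the RPC is already part of the randomised comparison. Their later outcomes are lost by rule, whether or not they would have answered.

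Two features make this loss less benign than ordinary non-response. First, the reason for it is close to what is being measured: the primary endpoints in Protocol 1.2 are changes in "policy knowledge and skills, policy engagement, and the extent to which research activities are informed by" public officials' needs. Second, the arms differ in what there is to stop. The RPC arm has six webinars, requests to contribute to policy work and possibly a Rapid Response Event. For the other arm, "The control group will receive information sheets regarding how to engage in policy". If stopping is related to outcome and its frequency differs by arm, the comparison of those who remain is shifted.

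There is also a practical problem. Someone following 3.3.1 and 3.3.2 would cease contact with a person who stops the RPC; someone following 7.2.2 would keep sending reminders.

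**Working it through.** **1. What happens to a researcher who stops the RPC but has not opted out of the surveys.**

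- Protocol 3.3.1: removed from the study.
- Protocol 3.3.2: not followed up.
- Protocol 7.2.2: reminders end on completion, close of the window or survey opt-out; stopping the RPC is not listed.
- Protocol 7.3: participation ends at up to two years or on study opt-out; stopping the RPC is not listed.

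Only 3.3.1 and 3.3.2 address the case, and they end data collection. The others are not aligned with them, though they do not strictly contradict them. Nothing says that data already collected are discarded, so earlier waves remain available to the models and to imputation.

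**2. The plan's own numbers (Protocol 16.2; SAP, Sample Size Justification).** 300 × 3/4 = 225 at baseline; 225 × 1/2 = 112.5, stated as 112 completers. This reproduces. The documents do not say how many of the roughly 113 non-completers would be lost through stopping the RPC.

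**3. Illustration of possible bias.** The documents give none of these inputs; all are assumptions:

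- s, share of an arm that stops: 5%, 10% or 20%.
- r, correlation of the tendency to keep going with the outcome, and equally with the baseline value: 0.2 to 0.4.
- ρ, correlation of baseline with outcome: 0.5 to 0.7.

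Stopping occurs when a normal latent trait falls below its s-quantile z = Φ⁻¹(s). Among those who continue, the mean of the trait is m = φ(z)/(1 − s). With k = m(m − z), their observed outcome mean is too high by r·m. After regression imputation on baseline, r·m·(1 − b) remains, where b = (ρ − r²k)/(1 − r²k).

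| s | z | m | k |
|---|---|---|---|
| 5% | −1.645 | 0.109 | 0.190 |
| 10% | −1.282 | 0.195 | 0.288 |
| 20% | −0.842 | 0.350 | 0.417 |

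Worked case, 20% against 5%, r = 0.4, ρ = 0.5:

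- Before imputation: 0.4 × (0.350 − 0.109) ≈ 0.097 SD.
- 20% arm: b = (0.5 − 0.16 × 0.417)/(1 − 0.16 × 0.417) = 0.464, leaving 0.4 × 0.350 × 0.536 = 0.075.
- 5% arm: b = 0.484, leaving 0.4 × 0.109 × 0.516 = 0.022.
- Difference after imputation: about 0.053 SD.

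Shift in the arm difference, in SD:

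| Stopping | r | Before imputation | After, ρ = 0.5 | After, ρ = 0.7 |
|---|---|---|---|---|
| 10% v 5% | 0.2 | 0.017 | 0.009 | 0.005 |
| 10% v 5% | 0.4 | 0.035 | 0.019 | 0.011 |
| 20% v 5% | 0.2 | 0.048 | 0.025 | 0.015 |
| 20% v 5% | 0.4 | 0.097 | 0.053 | 0.032 |

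Swapping the arms reverses the sign; equal shares with equal selection give 0. A simulation of 4,000,000 agrees to within 0.0002. Imputing from intermediate waves as well could shrink the shift further.

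**4. What continued surveys would recover.** If a random half of stoppers still answered, the simulated shift removed is about 0.003 to 0.011 SD (10% v 5%) or 0.009 to 0.032 SD (20% v 5%).

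**5. Binary scale.** The SAP plans logistic models, to which SD shifts do not carry over directly. As a rough guide, at an assumed 50% event rate, Φ(shift) − 0.5 gives 0.2 to 0.7 percentage points (10% v 5%) and 0.6 to 2.1 (20% v 5%).

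**6. Headcount.** With 225 at baseline and equal allocation, about 112 per arm: 5%, 10% and 20% are about 6, 11 and 22 researchers.

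**The case against.** The strongest reply is about weight. The webinars are voluntary and Protocol 8.1 expects incomplete participation without saying that such people leave the study. Low engagement alone therefore does not trigger removal; only an active choice to quit does. That group is undefined and may be very small, and people who quit may also decline the surveys. On this view the operative sections, 7.2.2 and 7.3, already describe the right practice, and what remains is an ambiguity. Controls also enlisted in the RPC and do not know their arm, so they too can stop; different activities do not establish different stopping rates. Finally, every input to the illustration is assumed, it ignores overlap with the much larger general attrition, and its range is not a bound. With r = 0.6, for example, 20% against 5% at ρ = 0.5 gives 0.089 SD.

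Most of this stands as a limit on size. Bias is possible and has not been shown, its direction is unknown, and the illustration is not evidence about this trial. It does not remove the rule. No section says that people who leave the RPC continue to be surveyed, and 3.3.1 with 3.3.2 says the opposite. Imputation and oversampling do not replace the uncollected outcomes: the first recovers only part from earlier waves, and the second adds other people.

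**Conclusion.** The concern holds. As written, the protocol ends outcome collection for randomised researchers who stop the intervention, for a reason close to a primary endpoint and with different activities to stop in each arm. The number affected is not given and may be small.

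Under the assumed stopping shares and correlations, the shift after imputation from baseline is about 0.005 to 0.053 SD. For scale, the planned effect size in Protocol 8.2 is 0.2, with its metric not stated. The sign could go either way, and equal loss with equal selection gives zero. This should be fixed because the loss is avoidable at little cost and the sections need aligning in any case, not because a large bias has been demonstrated. Confidence is medium, since the size depends entirely on assumptions.

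**What to change.** - **Protocol 3.3.1:** delete the last four words of "Researchers who choose to stop participating in the study or the RPC itself", so that only leaving the study leads to removal.
- **Protocol 3.3.2:** state that participants who stop RPC activities are still invited to every remaining survey unless they withdraw from the study or the surveys.
- **Protocol 7.2.2 and 7.3:** use the same rule and wording.
- **Reporting:** give RPC stopping, and survey completion among those who stop, by arm and wave.
- **Protocol 8.3 and SAP, Data Analysis Plan:** while amending, add that all randomised researchers are analysed in their assigned arm whatever their RPC participation. Neither document says so; this is a useful addition and not part of the case above.

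The cost is mainly wording. Reminders are already planned in 7.2.2, and participants keep their full right to opt out. At $10 per survey (Protocol 14.0) and at most three remaining surveys, the maximum is $30 per stopper. With 11 + 6 = 17 stoppers that is 17 × $30 = $510; with 22 + 6 = 28 it is 28 × $30 = $840. The effect on the estimated difference cannot be predicted in either direction.
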